**PROTOCOL VERSION: V2.0** 

## STUDY SUMMARY

TITLE Prospective Multi-Center Study on Vanguard Knee with E1 Bearing

**DESIGN** Prospective Observational Study

PURPOSE Evaluate Clinical Performance of Vanguard Knee with E1 Bearing in Korean

Patient Population

OUTCOME MEASURES Clinical Outcomes (e.g. KSS, KOOS, EQ5D, UCLA), Radiographic

Assessment and Survivorship

**POPULATION** 200

**ELIGIBILITY** Approved Indications for Uses for Vanguard Knee with E1 Bearing in TKA

**DURATION** 11 years

## INTRODUCTION

#### 1.1. BACKGROUND

## **E1**™

Vitamin E doping of highly cross-linked polyethylene is a proposed method for insuring long-term oxidative stability of highly cross-linked ultra-high molecular weight polyethylene for use in total joint arthroplasty. In vitro research and development studies have shown that this material has improved wear performance, retention of mechanical properties, and a high resistance to oxidation due to the anti-oxidative properties of Vitamin E. Biomet Inc, has received FDA clearance to market tibial polyethylene components made of E1™ for use in the Vanguard total knee replacement system.

## Vanguard Total Knee System™

The Vanguard™ Knee System was designed to incorporate features from prior designs, including: ACG, Maxim, & Ascent. The Vanguard Knee includes a streamlined design, rounded sagittal profile, and a deeper trochlear groove. The femoral component is available in Cruciate Retaining (CR), Posterior Stabilizing (PS), and Super Stabilized (SSK). Tibial Bearings are available in various levels of constraint required by the surgeon (CR, PS, AS, etc.).

For this study, ONLY Vanguard with PS Bearing will be used.

#### 1.2. RATIONALE FOR CURRENT STUDY

It is important to conduct a detailed clinical follow-up study when materials or implant designs are introduced for clinical use. Validated patient administered questionnaires allow for functional assessment, patient satisfaction and cost effectiveness analysis. These well established assessment techniques are well suited for evaluating large patient populations collected in multi-center studies of patients receiving total knee replacements.

#### 1.3. PURPOSES

The purpose of the study is to evaluate clinical performance of Vanguard Knee with E1 Bearing in TKA in Korean patient population. The clinical performance will be evaluated based on patient outcomes, radiographic assessment and survivorship.

## 2. STUDY DESIGN

## 2.1. OVERALL DESIGN

This study will be a multi-center observational study on patients with Vanguard Knee with E1 Bearing implanted. Patient demographic, preoperative clinical outcomes and operative information will be collected prospectively per defined follow-up intervals..

#### 2.2. STUDY GROUPS/TREATMENTS

Group 1 - patients who have received Vanguard Knee with E1 Bearing

#### 2.3. NUMBER OF SITES AND SUBJECTS/PROCEDURES

There are 4 sites in Korea to participate in this study.

#### 2.4. EFFICACY AND/OR SAFETY HYPOTHESES where appropriate

NA

#### 2.5. PRIMARY AND SECONDARY ENDPOINTS

Primary endpoint is KSS score at 1 year follow-up.

Secondary endpoints include

- KSS at other follow-up visits
- KOOS, EQ5D, UCLA at 6 month, 1 year, 3 year, 5 year postop
- Radiographic Assessment at Immediate postop, 1 year, 3 year, 5 year postop
- Survivorship up to 10 years

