#### Clinical Assessments

Clinical assessments will include functional scores and radiographic analysis. An operative record will be completed upon the surgery. The operative record will include but are not restricted to date of surgery, surgical approach, and implant components (part number).

Phone Assessment: If a patient will not or is not able to return to the office for a clinical exam, the patient administered outcome forms can be assessed with the patient over the phone. These forms include the KOOS, EQ-5D, UCLA Activity Score, and the Phone Interview (which contains questions on survivorship, KSS Pain, and KSS Function). If the site collects data over the phone, it will be reimbursed at a discounted rate to reflect the uncollected data (KSS Objective and Radiographic Assessment). At the seven and ten year follow-up, it is not required that the patient return for clinical assessment. At minimum, the Phone Interview Form should be collected to document survivorship.

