#### 6. STATISTICAL ANALYSIS PLAN

#### 6.1. SAMPLE SIZE CALCULATION

200 Cases is determined based on a confidence interval around the mean KSS objective score at 1 year.

The width of confidence interval is 5 points. The standard deviation is 18 points.

Total number of cases = 199 cases which is rounded to 200 cases.

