#### 6.5. DATA ANALYSES

The following analyses will be performed:

- 1. Primary Endpoint mean KSS Objective score at 1 year
- 2. Second Endpoints mean KSS Objective score at other postop time points
- 3. Other Clinical Outcomes scores including KOOS, EQ5D and UCLA
- Comparison in clinical outcomes scores between preoperative and various postoperative time points
- 5. Survivorship of Vanguard with endpoint being revisions.

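### Does calling the primary endpoint KSS score in section 2.5, but KSS Objective score in sections 6.1 and 6.5, leave the primary outcome undecided?

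*Protocol*

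**What the plan says.** Section 2.5 gives the primary endpoint in general terms: "Primary endpoint is KSS score at 1 year follow-up". Its first secondary endpoint is equally general: "KSS at other follow-up visits".

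The statistical sections are specific. Section 6.1 says "200 Cases is determined based on a confidence interval around the mean KSS objective score at 1 year", with an SD of 18 points and an interval width of 5 points. Section 6.5 lists "Primary Endpoint mean KSS Objective score at 1 year" as its first analysis and "mean KSS Objective score at other postop time points" as its second. Its third and fourth items cover other clinical outcome scores and the comparison of scores before and after surgery.

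The Clinical Assessments text in section 2.6.1 shows that the KSS has parts. The telephone form is described as one "which contains questions on survivorship, KSS Pain, and KSS Function", and KSS Objective is named there, with radiographs, as data that a telephone contact does not collect. The schedule in section 2.6.2 allows a telephone assessment at 6 months and at 1, 3 and 5 years for a patient who will not come to clinic. Section 6.4 imputes missing clinical scores by last observation carried forward.

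**The concern.** A single-arm study without a hypothesis (section 2.4 is marked not applicable) relies on one fixed primary score to prevent the result from being chosen after the data are seen. The section that formally defines the endpoints does not say which part of the KSS it means, and the protocol itself treats the parts as separately collectable. On its face, someone could report Function, or some total, and cite section 2.5 as authority.

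The telephone option appears to raise the stakes. A patient assessed by telephone at 1 year has Pain and Function but not Objective, so the definition might decide whether that patient is observed or imputed. At an assumed 10% to 20% of telephone visits, that would be 20 to 40 of the 200 cases. The planning SD and width are also tied to Objective, and no SD is given for any other KSS score. Finally, section 6.5 does not name Function or Pain, so they can look like data collected for no stated purpose.

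**Working it through.** **1. Do the sections conflict, or differ only in detail?**

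| Section | Role | Score named |
|---|---|---|
| 2.5, primary | endpoint list | KSS, no part named |
| 6.1 | sample size | KSS Objective, mean at 1 year |
| 6.5, item 1 | primary analysis | KSS Objective, mean at 1 year |
| 2.5, secondary | endpoint list | KSS, no part named |
| 6.5, item 2 | secondary analysis | KSS Objective at other postoperative times |

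KSS Objective is a KSS score, so reporting it satisfies all five rows. No row names Function, Pain or a total as primary, and the protocol nowhere mentions a total. Section 6.5 labels its first item as the primary endpoint, so the choice is already fixed in writing before any data.

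**2. Does the sample size agree with that reading?** The inputs from section 6.1 are SD 18 and width 5. The confidence level is not stated; I assume 95%, two-sided.

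n = (z × SD / half-width)² = (1.95996 × 18 / 2.5)² = 199.14

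This reproduces the stated 199, rounded to 200. Taking 5 as the half-width gives 49.8, which does not. The planned precision therefore belongs to KSS Objective, with 5 as the full width, and reading section 2.5 as Objective leaves it unchanged. With 200 observed cases the full width is 2 × 1.95996 × 18 / √200 = 4.99.

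A different score with a different SD would need a different number. For assumed SDs of 15, 20, 25 and 30 the same formula gives 139, 246, 385 and 554. Those figures matter only if another score is primary, which no section says.

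**3. What does a 1-year telephone visit supply under each reading?**

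| Reading of the primary score | Observed value by telephone? |
|---|---|
| Objective (6.1, 6.5) | no |
| A total that needs Objective | no |
| Function alone | yes |
| Pain alone | yes |

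The patient's status changes only in the last two rows, and neither reading has support in the document. It is therefore not true that every telephone patient switches between observed and missing.

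**4. How much precision do telephone visits cost under Objective?** With an assumed 10% or 20% of the 200 cases lacking an observed value, 180 or 160 remain. The full widths are:

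- 2 × 1.95996 × 18 / √180 = 5.26
- 2 × 1.95996 × 18 / √160 = 5.58

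This loss comes from the telephone option itself. It is the same whether or not the word Objective stands in section 2.5.

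**5. Are Function and Pain left without an analysis?** Item 3 of section 6.5 introduces KOOS, EQ5D and UCLA with the word including, so that list is open. Item 4 compares clinical outcome scores over time without restricting which ones. The study summary and the schedule both count the KSS, undivided, among the clinical outcomes. Function and Pain are not named, but they fit under items 3 and 4.

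**The case for a change.** The best case for a change is that this goes beyond missing detail. The protocol states its primary endpoint twice, in different words, and the broader statement sits in the section a reader consults for endpoints. The protocol divides the KSS in its own telephone procedure, so the undivided term is not self-explanatory. The difference also touches the secondary endpoint. At 7 and 10 years the minimum contact is a telephone interview, which can yield Pain and Function but not Objective, so the general wording in section 2.5 could take in data that item 2 of section 6.5 cannot. A correction would cost a few words.

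Part of this stands. The wording does differ, section 2.5 is the looser text, and the status of Function and Pain is left to inference. What does not stand is the step from there to an open primary outcome. That step needs a reader to set aside sections 6.1 and 6.5, which agree with each other, in favour of a score that no section makes primary. How the KSS parts are set out as secondary results is ordinary content for a statistical analysis plan, which is not at hand. The case report forms, which would show how the score is recorded, are a separate attachment.

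**Conclusion.** No change to the plan follows. The mismatch is a clerical difference between a general and a specific name for the same endpoint, and analysts would resolve it one way: mean KSS Objective at 1 year, with its confidence interval. Under that reading the sample size stays at 199, rounded to 200, the primary analysis is as listed in section 6.5, and a patient seen only by telephone at 1 year has no observed primary value.

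Adding the word Objective to section 2.5 would tidy the text but would alter no result or conclusion. Naming Function and Pain as secondary endpoints would add detail that section 6.5 already has room for.

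This rests on two assumptions: that the unstated confidence level is 95%, which the reproduced sample size supports, and that no document outside the protocol makes another KSS score primary. The 10% to 20% telephone rate is illustrative, since the protocol gives none, and the verdict does not depend on it.

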#### 2.6.2. ASSESSMENT TIMELINES/SCHEDULE

Clinical and Radiographic Exams									
Data Collection item	Pre- operati ve	Intra- operati ve	Immediate Post- operative	6 Months	1 Year	3 years	5 years	7 years	10 years
Demographic and Medical History	Х								
Operative Record		×							
Clinical Evaluation – KSS, KOOS, EQ5D, UCLA	х			х	х	х	х		
Radiographic assessment			х	Х	х	х	х		
Phone Assessment				If Patient will not come to clinic	If Patient will not come to clinic	If Patient will not come to clinic	If Patient will not come to clinic	×	X
Adverse events including revisions		As required							

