## **Appendix A: Radiographic Protocol**

A series of three, required radiographs are to be taken at each designated interval as follows: 1) Standing Anteroposterior Knee, 2) Lateral Supine Knee, and 3) Sunrise Patella view.

View	Positioning the Patient	Proper Alignment	Radiograph
1) Standing Anteroposterio r	The patient should be standing upright, bearing weight on the side of the affected knee. The central ray is horizontal and perpendicular to the center of the cassette.	Proper alignment can be achieved by directing the central ray approximately ½ inch inferior to the apex of the patella.	In a proper AP film, the femorotibial joint space should be clearly visible at the center of the radiograph with equal interspaces on each side, and the patella should be completely superimposed on the femur.
2) Lateral Supine	The patient should lie down and turn onto the affected side so that the pelvis lies perpendicular to the exam table. The affected knee should be extended forward and bent at a flexion of 20 to 30 degrees to ensure the patient's muscles are relaxed.	Ideal alignment can be achieved by adjusting the epicondyles so that they lie perpendicular to the IR. The central ray should be directed 1 inch distal to the medial epicondyle at an angle of 5-7 degrees cephalad.	In a proper lateral X-ray, the femorotibial joint space should be clearly visible at the center of the radiograph, and the patella should be unimpeded by the femoral component.
3) Sunrise Patella	The patient should be placed in a seated position, holding the 8 x10 cassette securely in place along the mid-thigh. The degree of optimal flexion varies patient by patient, but is typically minimal.	Proper positioning will show articulating surfaces	In a proper Sunrise X-ray, the articulating surfaces of the patella and femoral condyles should be clearly visible

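### Do the differing radiograph time points in sections 2.5 and 2.6.2, and the absence of a radiographic item in section 6.5, call for a change to the plan?

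*Protocol*

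**What the plan says.** Section 1.3 of the protocol sets the purpose: "The clinical performance will be evaluated based on patient outcomes, radiographic assessment and survivorship". Section 2.5 then lists, among the secondary endpoints, "Radiographic Assessment at Immediate postop, 1 year, 3 year, 5 year postop". A neighbouring entry in the same list reads "KOOS, EQ5D, UCLA at 6 month, 1 year, 3 year, 5 year postop", so 6 months is named for the questionnaires and not for the films.

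In the section 2.6.2 table, the row headed "Radiographic assessment" is marked at immediate postop, 6 months, 1 year, 3 years and 5 years. Appendix A gives the imaging technique and says "A series of three, required radiographs are to be taken at each designated interval as follows", without listing the intervals.

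Section 6.5 opens with "The following analyses will be performed" and gives five items: mean KSS Objective at 1 year; mean KSS Objective at other postoperative times; "Other Clinical Outcomes scores including KOOS, EQ5D and UCLA"; comparison of scores before and after surgery; and survivorship with revision as the event. None mentions radiographs.

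**The concern.** The same assessment has two sets of time points, and Appendix A does not settle which applies. If some of the four sites worked from section 2.5 and others from section 2.6.2, 6-month films would exist at some sites and not at others. Early radiographic findings would then have unequal chances of being seen. An analyst might also not know whether a 6-month film counts as endpoint data.

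The second worry is that section 6.5 reads like a complete list. Taken literally, it would leave one of the three stated bases of evaluation unreported.

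**Working it through.** **The plan's own figure.** The only calculated quantity in the protocol is the sample size in section 6.1. Inputs: "The standard deviation is 18 points" and a full confidence-interval width of 5 points, so a half-width of 2.5. The confidence level is not stated; I assume 95% two-sided, z = 1.95996.

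n = (z × SD / half-width)² = (1.95996 × 18 / 2.5)² = (14.1117)² = 199.14

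This agrees with the stated 199, rounded to 200. It concerns KSS Objective at 1 year, and no radiographic quantity enters it.

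**Time points side by side.**

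| Time point | Endpoint (2.5) | Schedule (2.6.2) |
|---|---|---|
| Immediate postop | yes | yes |
| 6 months | no | yes |
| 1 year | yes | yes |
| 3 years | yes | yes |
| 5 years | yes | yes |
| Total | 4 | 5 |

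The difference is exactly one visit, and it runs in one direction. Every endpoint time point is scheduled (4 of 4); one scheduled time point is not a named endpoint (1 of 5). The reverse case, an endpoint with no scheduled film, would be a real defect, because the endpoint could not be analysed. It does not occur.

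**Which text directs the sites.** Section 2.5 says what will be evaluated, and its wording presents the secondary endpoints as a list that need not be exhaustive. It neither orders nor forbids any film. Section 2.6.1 sends the reader to Appendix A for radiographs. Appendix A refers to designated intervals, and the table in section 2.6.2 is the only place that assigns radiographs to visits as a collection schedule. The phone-assessment text in section 2.6.1 fits this: it counts radiographs among the data lost when a visit is done by phone, and the table allows phone assessment at 6 months. Collecting a measurement at a visit that is not a named endpoint is not in itself a contradiction.

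**Size.** With three views per interval, the 6-month visit involves at most 200 × 3 = 600 films, out of at most 5 × 600 = 3,000 scheduled. The share is 600 / 3,000 = 20%. This is a ceiling, since it assumes every case attends in person at 6 months. It counts films; it is not a bias or a loss of precision.

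**What the 6-month film could affect.**

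- Primary endpoint: KSS at 1 year. Not affected.
- Survivorship: defined by revisions. The definition uses no film.
- Error rates: section 2.4 states no hypotheses, so counting or not counting 6 months as an endpoint spends no alpha.
- Group comparison: section 2.2 has a single group, so there is no between-arm detection bias to create.

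**Section 6.5.** Radiographic items: 0 of 5. The list does not say that films will go unanalysed, and it does not exclude further analyses. It is also terse elsewhere: section 2.5 names KSS at other visits, whereas the matching item in section 6.5 names only KSS Objective. One absent line in a summary of this kind is weak evidence that radiographs were meant to be dropped.

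**The case for a change.** The strongest case for a change is that section 2.5 is not using shorthand. It names 6 months for the questionnaires and leaves it out for films, so the difference is specific to radiographs and nothing in the protocol explains it. It may have practical effects: section 2.6.1 reduces the payment for phone visits partly because films are not collected, and section 4 requires deviations to be documented. Whether a missing 6-month film counts in either case could be argued from section 2.5. In addition, section 6 of the protocol is itself headed as the statistical analysis plan, and radiographic assessment is the one entry in section 2.5 with no counterpart in section 6.5.

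Part of this stands. The two passages differ, and the protocol does not say whether the 6-month films are endpoint data. The sponsor can reconcile them, and I take no view on which set of time points should remain.

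The consequences drawn from it do not stand. Uneven imaging across sites requires a site to ignore the visit schedule and work from an endpoint list, and nothing in the protocol suggests that any would. The payment and deviation questions are administrative and are answered by the schedule. For the analyst, section 6.5 is silent and gives no opposing instruction. Radiographic analysis detail is commonly placed in a separate analysis plan, which may exist and is not at hand.

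**Conclusion.** No change to the plan follows. The mismatch is real but editorial: one visit, at most 600 films, and all four named radiographic endpoint time points remain scheduled and analysable. The missing radiographic line in section 6.5 is a gap that an analyst would fill from sections 1.3 and 2.5. Aligning the wording would make the protocol tidier but would alter no estimate, interval, sample size or conclusion.

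This rests on two assumptions: that sites collect according to the schedule in section 2.6.2, and that radiographs are analysed as the stated purpose and endpoint list imply. If a final report omitted radiographs altogether, that would be a reporting failure against sections 1.3 and 2.5, which already name them.

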#### 2.6. ASSESSMENT PROCEDURE

#### 2.6.1. ASESSMENT PARAMETERS AND METHODS

#### Medical History and Demographic Data

Demographic information will be collected which will include but is not limited to gender, age at surgery, height, weight, primary diagnosis & medical history

#### Clinical Assessments

Clinical assessments will include functional scores and radiographic analysis. An operative record will be completed upon the surgery. The operative record will include but are not restricted to date of surgery, surgical approach, and implant components (part number).

Phone Assessment: If a patient will not or is not able to return to the office for a clinical exam, the patient administered outcome forms can be assessed with the patient over the phone. These forms include the KOOS, EQ-5D, UCLA Activity Score, and the Phone Interview (which contains questions on survivorship, KSS Pain, and KSS Function). If the site collects data over the phone, it will be reimbursed at a discounted rate to reflect the uncollected data (KSS Objective and Radiographic Assessment). At the seven and ten year follow-up, it is not required that the patient return for clinical assessment. At minimum, the Phone Interview Form should be collected to document survivorship.

#### Radiographic Assessments

Radiographic assessments will be conducted based on Radiographic Assessment protocol in Appendix A.

#### 2.6.2. ASSESSMENT TIMELINES/SCHEDULE

Clinical and Radiographic Exams									
Data Collection item	Pre- operati ve	Intra- operati ve	Immediate Post- operative	6 Months	1 Year	3 years	5 years	7 years	10 years
Demographic and Medical History	Х								
Operative Record		×							
Clinical Evaluation – KSS, KOOS, EQ5D, UCLA	х			х	х	х	х		
Radiographic assessment			х	Х	х	х	х		
Phone Assessment				If Patient will not come to clinic	If Patient will not come to clinic	If Patient will not come to clinic	If Patient will not come to clinic	×	X
Adverse events including revisions		As required							

#### 2.6.3. ALLOWED WINDOW OF EACH SCHEDULE

Allowed Window of Each Prospective Visit Schedule:

- 6 months (+/- 2 weeks)
- 12 months (+/- 2 months)
- 3 years (+/- 3 months)
- 5 years (+/- 3 months)
- 7 years (+/- 3 months)
- 10 years (+/- 3 months)

Each follow-up visit time point will be determined based on the date of surgery.

Investigators should make their best effort to have patients return in the allotted time window of each milestone. However, in the event that patients return outside of the milestone, the data should still be recorded and reimbursed. Visits will only be reimbursed once per milestone.

